#### 4.5. Standard Calculations

Variables requiring calculation will be derived using the following formulas:

- Days – A duration expressed in days between one date (*date1*) and another later date (*date2*) will be calculated using the following formulas:
  - duration in days =  $date2 - date1 + 1$ , where  $date1 \geq$  first administration date
  - duration in days =  $date2 - date1$ , where  $date1 <$  first administration date
- Months – A duration expressed in months is calculated as the number of days divided by 30.4375
- Years – A duration expressed in years between one date (*date1*) and another date (*date2*) is calculated using the following formulas:
  - duration in years =  $(date2 - date1 + 1)/365.25$ , where  $date1 \geq$  first administration date
  - duration in years =  $(date2 - date1)/365.25$ , where  $date1 <$  first administration date
- Body Mass Index (BMI) – BMI is calculated using height (cm) and weight (kg) using the following formula:
$$BMI \text{ (kg/m}^2\text{)} = \text{weight (kg)} / ([\text{height (cm)} / 100]^2)$$

- Change (CHG; equivalent to absolute change for liver fat content [LFC]) – Change will be calculated as:

Change = later value – earlier (i.e., baseline) value

- Percent change (PCHG; equivalent to relative change for LFC) – Percent change will be calculated as:

Percent change = ([Change] / earlier [i.e., baseline] value) × 100

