#### **8.8.4.3. Statistical Methods for PD Parameters**

Plasma PD parameters will be summarized by treatment group using descriptive statistics (number of non-missing observations, arithmetic mean, SD, median, Q1, Q3, minimum, maximum, geometric mean, and geometric CV%).

For the calculation of summary statistics, all NR and not calculated (NC) values in a data series will be set to missing.

Analyses of pre-dose/trough values for plasma VAP-1/SSAO activity ( $A_{avg}$  and  $A_{min}$ ) and methylamine ( $C_{avg}$  and  $C_{max}$ ) at Week 0/Day 1, Week 6, and Week 12 will be carried out using an ANCOVA model with the PD parameter as the dependent variable including treatment group as a fixed effect and baseline VAP-1/SSAO activity or methylamine concentration as a covariate. The model will be carried out separately for the PD parameter based on the VAP-1/SSAO activity and methylamine value, change from baseline, and percent change from baseline. The estimates of LS means, SE, and 90% and 95% CIs will be presented by treatment group. Estimates of the LS mean difference for each pairwise comparison will be presented with associated the standard error of the difference, and 90% and 95% CIs of the difference.

The distribution of parameter values will be evaluated visually for normality assumptions. If normality assumptions are violated, first the data will be natural log transformed and the log transformed data evaluated for normality. If the log transformed data are normally distributed, the same ANOVA model described above will be used.

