The distribution of change (percent change) values will be evaluated visually for normality assumptions. If normality assumptions are violated, first the data will be natural log transformed and the log transformed data evaluated for normality. If the data are not normally distributed, a Wilcoxon Rank Sum Test will be used to compare treatment groups. The median differences and 90% and 95% CIs of the median differences between treatment groups will be constructed using Hodges-Lehmann estimate.

Sensitivity analyses using the PP and Treatment Completer Analysis Sets will be presented if the analysis set differs from the Efficacy Analysis Set by more than 10% total.

cT1 will be categorized as low (<800 msec), elevated (800 – 900 msec), and high (>900 msec). A shift table from baseline to Week 6 and baseline to Week 12 will be presented by treatment group.

In addition, cT1 responders will be defined as any patient with a decrease of at least 80 msec. Non-responders will be defined as any patient who did not have at least an 80 msec decrease. For both endpoints, the number and percentage, with associated two-sided exact (Clopper-Pearson) 90 and 95% CIs, of patients in each category will be presented by treatment group at each post-baseline visit. A Chi-square test at each post-baseline visit will be used to compare each pairwise comparison between placebo and each active dose of TERN-201.

The number and percentage of patients who are responders on cT1 and ALT will be summarized and analyzed in the same manner as responders.

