### **8.10.1.2. Liver Fat Content by MRI Proton Density Fat Fraction (PDFF)**

Liver fat content (LFC) or proton density fat fraction (PDFF) is an estimate of the percentage of fat within a tissue. It is defined as the proportion of the mobile proton density in the liver attributable to fat. PDFF is quantified from the ratio of fat/(fat+water) components in images and is expressed as a percentage (%). The PDFF metric on the quantitative analysis output is a summarized metric from the individual pixels within all of the region of interests (ROIs) placed on the PDFF parametric map or an average of all the pixels within the contour generated by automatic liver segmentation. The PDFF metric is displayed as a median and interquartile range (IQR), the median will be used in all analyses.

Analyses of liver fat content (LFC) by MRI by MRI-PDFF will be based on the Efficacy Analysis Set. For the purposes of LFC analyses, absolute change is equivalent to change and relative change is equivalent to percent change (see [Section 4.5](#)). Descriptive statistics of the LFC by MRI-PDFF results, absolute change from baseline, and relative change will be summarized by treatment group and visit.

LFC by MRI-PDFF will be analyzed in the same manner as LFC ([Section 8.10.1.1](#)). LFC by MRI-PDFF responders will be defined as any patient with a relative decrease of at least 30% (i.e.,  $\leq -30\%$ ). Non-responders will be defined as any patient who did not have at least a 30% relative decrease (i.e.,  $> -30\%$ ). The number and percentage, with associated two-sided exact (Clopper-Pearson) 90% and 95% CIs, of patients in each category (response, nonresponse) will

be presented by treatment group at Week 6 and Week 12. A Chi-square test at Week 6 and Week 12 will be used to compare each pairwise comparison between placebo and each active dose of TERN-201.

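### The normality fallback takes the natural log of change and percent-change values, which is undefined for every patient whose value falls or stays the same, including every cT1 and liver-fat responder

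*SAP*

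**What the plan says.** SAP 8.10.1.1 (cT1) fits an ANCOVA to change and, separately, to percent change from baseline, with treatment and randomization strata as fixed effects and baseline as covariate. The fallback has three steps:

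1. "The distribution of change (percent change) values will be evaluated visually for normality assumptions".
2. "If normality assumptions are violated, first the data will be natural log transformed and the log transformed data evaluated for normality".
3. "If the data are not normally distributed, a Wilcoxon Rank Sum Test will be used to compare treatment groups", with Hodges-Lehmann estimates and intervals.

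SAP 4.5 gives the definition "Change = later value – earlier (i.e., baseline) value"; percent change is that quantity divided by baseline, times 100.

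The rule reaches liver fat (8.10.1.2), liver stiffness (8.10.2), AST, ALT and GGT (8.10.3), ALT change from end of treatment (8.10.3.1), the fibrosis markers and scores (8.10.4), and, through 8.10.4, the inflammation markers (8.10.5), proteinuria markers (8.10.6) and weight (8.10.7).

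SAP 8.8.4.3 has a parallel rule for the sub-study pharmacodynamic parameters, whose model is run "separately for the PD parameter based on the VAP-1/SSAO activity and methylamine value, change from baseline, and percent change from baseline". It ends with: "If the log transformed data are normally distributed, the same ANOVA model described above will be used". It does not say what happens if they are not.

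**The concern.** The only data named before the log step in 8.10.1.1 are change and percent-change values, which are also the dependent variables of the model. These are signed quantities, so the instruction cannot be carried out for anyone who fell or stayed level.

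For most of these endpoints a fall is improvement, so the patients with no log value are the ones who did well. For endpoints expected to rise, or to improve by rising (methylamine, eGFR), the patients lost are those who decline.

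A programmer has three ways out: log only the patients who rose, log the raw values instead, or declare the step failed. They give different estimates. Markers such as hs-CRP, IL-6, UACR and UPCR are plausibly skewed enough to trigger the rule. The check is visual, and the SAP does not say when it is made or whether on pooled data. SAP 8.3 has Part 1 locked, unblinded and analysed on its own, so the choice could be made with treatment known.

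**Working it through.** **No plan figure to reproduce.** The sample size was set without regard to power, and the SAP gives no number on this point. The check is whether the logarithm exists, followed by illustrations.

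**Does the log exist at the SAP's own cut-offs?** ln(x) requires x > 0.

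| Case | Source | Value | ln |
|---|---|---|---|
| cT1, smallest response | 8.10.1.1: "cT1 responders will be defined as any patient with a decrease of at least 80 msec" | -80 msec | undefined |
| Liver fat, smallest response | 8.10.1.2: "LFC by MRI-PDFF responders will be defined as any patient with a relative decrease of at least 30" percent | -30% | undefined |
| No change | 4.5 | 0 | undefined |
| VAP-1/SSAO suppressed by 80% or 90% | Protocol 2.2.2, first-in-human results | -80%, -90% | undefined |
| cT1 rise of 10 msec | example | +10 msec | 2.303 |

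All cT1 and liver-fat responders therefore lie outside the domain. This needs no assumption.

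**SAP 8.8.4.3.** The log works on the value scale. It fails on the two change scales for VAP-1/SSAO: at about 90% suppression, about 0 of the 8 treated Part 1 sub-study patients have a usable value. On Day 1 the failure is built in. Baseline is the Day 1 pre-dose value (4.7.2) and the Day 1 profile includes the pre-dose sample (8.8.4), so the minimum change is zero or negative for every patient, placebo included.

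**If undefined values are set to missing.** Assume normal percent change with mean -20 on active and 0 on placebo. The documents give no SDs, so a range is shown. The undefined share is Φ(-mean/SD), for example Φ(20/20) = 0.841. For placebo it is 0.50, leaving 5 of 10.

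| SD | Active undefined | Active kept of 20 | Mean % change among kept, active vs placebo | Difference (true -20) | Difference in mean ln among kept |
|---|---|---|---|---|---|
| 20 | 84.1% | 3.2 | 10.5 vs 16.0 | -5.5 | -0.49 |
| 30 | 74.8% | 5.0 | 18.0 vs 23.9 | -6.0 | -0.34 |
| 40 | 69.1% | 6.2 | 25.6 vs 31.9 | -6.3 | -0.26 |

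The fifth column shows what selection does to the percent-change gap. The last column is the contrast that a logged analysis would report.

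**If the step is treated as failed.** The comparison is log-ratio ANCOVA against the SAP's Wilcoxon test. Assumptions: lognormal baseline and post-baseline values, correlation 0.7, true ratio 0.6, two-sided 0.05, 4,000 trials per setting, stratum omitted. Null rejection was 4.3 to 5.7% for all three methods.

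| Arms | Log-SD | Log-ratio ANCOVA | Wilcoxon, percent change | Wilcoxon, change |
|---|---|---|---|---|
| 20 vs 10 (Part 1) | 0.5 | 94% | 88% | 73% |
| | 0.8 | 57% | 48% | 36% |
| | 1.0 | 44% | 34% | 25% |
| 20 vs 20 (placebo pooled over both parts) | 0.5 | 99% | 97% | 91% |
| | 0.8 | 77% | 69% | 53% |
| | 1.0 | 57% | 49% | 36% |

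**With a log ratio.** Taking ln(post-baseline/baseline) instead, no change is 0, a 30% liver-fat fall is ln(0.7) = -0.357, a cT1 fall from 801 to 721 msec is -0.105, and 90% suppression is ln(0.1) = -2.303. Every patient with positive values is defined.

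**The case against.** The strongest reply is that no competent programmer would log a negative change. SAP 4.4 allows a variable with a non-normal distribution to be transformed, so the authors may have meant the measured value. Failing that, the Wilcoxon step uses every patient. The endpoints in 8.10 are exploratory, all testing is nominal (8.6), and the fallback applies only if the visual check fails.

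Part of this stands. The reach is limited: the primary safety endpoint, the 8.8.3 ANCOVA for the secondary endpoint, the cT1 and liver-fat responder analyses and the dose-response models of 8.8.4.4 and 8.10.8 have no such log step. Logging only the patients who rose is the worst case, not the expected one. The power comparison favours the log-ratio model because the data were simulated from it; against Wilcoxon on percent change the gap is only 2 to 10 points.

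The rest does not remove the defect. SAP 4.4 is optional and does not say which quantity is logged. If raw values were meant, the dependent variable and covariate would have to be restated. The SAP does not say that an undefined log counts as non-normal, and Wilcoxon drops the baseline covariate and the stratum. Section 8.8.4.3 has no Wilcoxon step.

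**Conclusion.** The concern holds. The log step in 8.10.1.1, and in 8.8.4.3 on the change scales, cannot be executed as written for any patient with a fall or no change. That conclusion follows from the SAP's own definitions alone.

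The shares lost, the shrunken differences and the power figures rest on assumed means, SDs, ratio and correlation; they show the possible scale and predict nothing about this trial. The practical harm is an undefined, possibly post-unblinding choice between analyses that disagree, across the preliminary-efficacy endpoints and the sub-study pharmacodynamic parameters. It should be fixed, but it does not threaten the primary objective.

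**What to change.** Replace the log step in 8.10.1.1 and 8.8.4.3 with wording such as:

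> If normality is violated, the analysis will use ln(post-baseline/baseline) as the dependent variable and ln(baseline) as covariate, with the other terms of the specified model unchanged (treatment and randomization strata in 8.10.1.1; treatment in 8.8.4.3). Results will be back-transformed to geometric mean ratios and percent change with 90% and 95% CIs.

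Then:

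- For ALT change from end of treatment, use ln(Week 16/end of treatment).
- In 8.8.4.3, use ln(PD parameter/baseline). Because this equals ln(parameter) - ln(baseline) and ln(baseline) is in the model, the treatment contrast is the same as for ln(parameter), and the three scales become one log analysis.
- Apply the rule to strictly positive measurements, including cT1, liver fat, stiffness, eGFR and weight. Keep the NAFLD fibrosis score, which can be zero or negative, and ELF, which is already logged, on their original scales.
- Keep Wilcoxon with Hodges-Lehmann as the last step, and add it to 8.8.4.3.
- Make the normality judgement on blinded pooled data, or name the log-scale analytes, before Part 1 is unblinded.

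Under strong suppression, VAP-1/SSAO results below quantification are set to half the limit (8.8.1). They stay positive, but the log ratio may then depend on that imputation, so the count of such values should be read beside it.

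The cost is SAP wording and modest reprogramming, with no new data. Analytes that trigger the rule are reported as ratios. Deleting the log step and going straight to the rank test would be simpler and would also be executable, but it gives up the baseline and stratum adjustment.

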### **8.10.1.2. Liver Fat Content by MRI Proton Density Fat Fraction (PDFF)**

Liver fat content (LFC) or proton density fat fraction (PDFF) is an estimate of the percentage of fat within a tissue. It is defined as the proportion of the mobile proton density in the liver attributable to fat. PDFF is quantified from the ratio of fat/(fat+water) components in images and is expressed as a percentage (%). The PDFF metric on the quantitative analysis output is a summarized metric from the individual pixels within all of the region of interests (ROIs) placed on the PDFF parametric map or an average of all the pixels within the contour generated by automatic liver segmentation. The PDFF metric is displayed as a median and interquartile range (IQR), the median will be used in all analyses.

Analyses of liver fat content (LFC) by MRI by MRI-PDFF will be based on the Efficacy Analysis Set. For the purposes of LFC analyses, absolute change is equivalent to change and relative change is equivalent to percent change (see [Section 4.5](#)). Descriptive statistics of the LFC by MRI-PDFF results, absolute change from baseline, and relative change will be summarized by treatment group and visit.

LFC by MRI-PDFF will be analyzed in the same manner as LFC ([Section 8.10.1.1](#)). LFC by MRI-PDFF responders will be defined as any patient with a relative decrease of at least 30% (i.e.,  $\leq -30\%$ ). Non-responders will be defined as any patient who did not have at least a 30% relative decrease (i.e.,  $> -30\%$ ). The number and percentage, with associated two-sided exact (Clopper-Pearson) 90% and 95% CIs, of patients in each category (response, nonresponse) will

be presented by treatment group at Week 6 and Week 12. A Chi-square test at Week 6 and Week 12 will be used to compare each pairwise comparison between placebo and each active dose of TERN-201.

### **8.10.2. Transient Elastography**

Liver stiffness and CAP are measured by transient elastography. Descriptive statistics of biomarker values, change from baseline, and percent change from baseline will be presented by treatment group for each visit, at which data are collected, using the Efficacy Analysis Set.

Change (and separately for percent change) from baseline in liver stiffness will be analyzed using the same ANCOVA model presented in [Section 8.10.1.1](#) for each post-baseline and follow up visit using observed data only. Sensitivity analyses using the PP and Treatment Completer Analysis Sets will be presented if the analysis set differs from the Efficacy Analysis Set by more than 10% total.

Assessments of normality will be performed as described in [Section 8.10.1.1](#).

### **8.10.3. Liver Function Tests**

LFTs for efficacy analyses include AST, ALT, and GGT. Descriptive statistics of LFT values, change from baseline, and percent change from baseline values will be presented by treatment group for each visit using the Efficacy Analysis Set.

Change (and separately for percent change) from baseline will be analyzed using the same ANCOVA model presented in [Section 8.10.1.1](#) for each post-baseline and follow up visit using observed data only. Sensitivity analyses using the PP and Treatment Completer Analysis Sets will be presented if the analysis set differs from the Efficacy Analysis Set by more than 10% total.

Assessments of normality will be performed as described in [Section 8.10.1.1](#).

Figures of LS mean ( $\pm$ SE) change from baseline, and percent change from the ANCOVA model will be presented over time by treatment group.

#### **8.10.3.1. Change from End of Treatment in ALT**

The change (and separately percent change) from end of treatment to follow up visit (Week 16) will be summarized by treatment group. For patients who complete Week 12, the Week 12 value will be used for End of Treatment. For patients who do not complete treatment, the last value on treatment will be used for End of Treatment. Descriptive statistics of ALT values, change from end of treatment, and percent change from end of treatment will be presented by treatment group for each visit using the Efficacy Analysis Set.

Change (and separately for percent change) from end of treatment in ALT will be analyzed using the same ANCOVA model presented in [Section 8.10.1.1](#) for each follow up visit using observed data only. Assessments of normality will be performed as described in [Section 8.10.1.1](#).

Sensitivity analyses using the PP and Treatment Completer Analysis Sets will be presented if the analysis set differs from the Efficacy Analysis Set by more than 10% total.

Sensitivity analyses will be conducted including only Week 16 assessments which are at least 22 days from last dose.

#### **8.10.4. NASH and Fibrosis Biomarkers**

Markers of hepatic fibrosis and apoptosis include CK-18 (M30 and M65), PIIINP, TIMP-1, HA, PRO-C3, and C3M. The PRO-C3/C3M ratio will be calculated. Descriptive statistics of biomarker values, change from baseline, and percent change from baseline will be presented by treatment group for each visit using the Efficacy Analysis Set.

Change (and separately for percent change) from baseline will be analyzed using the same ANCOVA model presented in [Section 8.10.1.1](#) for each post-baseline and follow up visit using observed data only. Sensitivity analyses using the PP and Treatment Completer Analysis Sets will be presented if the analysis set differs from the Efficacy Analysis Set by more than 10% total.

Assessments of normality will be performed as described in [Section 8.10.1.1](#).

##### **8.10.4.1. Enhanced Liver Fibrosis (ELF) Score**

The enhanced liver fibrosis (ELF) score will be calculated as:  $2.278 + 0.851 \ln(\text{HA}) + 0.751 \ln(\text{PIIINP}) + 0.394 \ln(\text{TIMP-1})$ . Lab values from the same visit will be used to calculate the ELF score. The ELF score will be calculated at baseline and each post-baseline visit.

The ELF score will be analyzed in the same manner as specified in [Section 8.10.4](#).

##### **8.10.4.2. Fibrosis-4 (FIB-4) Score**

The Fibrosis-4 (FIB-4) score helps to estimate the amount of scarring in the liver. The FIB-4 score is calculated as:  $[\text{Age (years)} \times \text{AST (U/L)}] \div [\text{Platelet Count (10}^9/\text{L}) \times \text{ALT (U/L)}^{0.5}]$ . Age at screening will be used. Lab values at each visit, from the same visit, will be used. The FIB-4 score will be calculated at baseline and each post-baseline visit.

The FIB-4 score will be analyzed in the same manner as specified in [Section 8.10.4](#).

##### **8.10.4.3. Nonalcoholic Fatty Liver Disease (NAFLD) Fibrosis Score**

The Nonalcoholic Fatty Liver Disease (NAFLD) fibrosis score will be calculated as:  $-1.675 + 0.037 \times \text{Age (years)} + 0.094 \times \text{BMI (kg/m}^2) + 1.13 \times \text{diabetes status (yes = 1, no = 0)} + 0.99 \times \text{AST/ALT ratio} - 0.013 \times \text{Platelet Count (10}^9/\text{L}) - 0.66 \times \text{Albumin (g/dL)}$ . Age and diabetes status at informed consent will be used. BMI at each visit will be calculated using the weight from that visit and height from screening. Lab values at each visit, from the same visit, will be used. The NAFLD fibrosis score will be calculated at baseline and each post-baseline visit.

The NAFLD fibrosis score will be analyzed in the same manner as specified in [Section 8.10.4](#).

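### The NAFLD fibrosis score can be negative, zero or positive, yet the SAP analyses its percent change over the signed baseline, so that one output for an exploratory score cannot be interpreted

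*SAP*

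**What the plan says.** SAP 8.10.4.3 builds the NFS from a constant of -1.675, positive weights on age, BMI, diabetes and the AST/ALT ratio, and negative weights on platelets and albumin. On analysis it says: "The NAFLD fibrosis score will be analyzed in the same manner as specified in" Section 8.10.4.

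SAP 8.10.4 asks for descriptive statistics of values, change and percent change, and then: "Change (and separately for percent change) from baseline will be analyzed using the same ANCOVA model presented in" Section 8.10.1.1. The two outcomes are defined in SAP 4.5:

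- "Change = later value – earlier (i.e., baseline) value"
- "Percent change = ([Change] / earlier [i.e., baseline] value) × 100"

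The divisor is the baseline with its sign. Nothing exempts a score that can cross zero.

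The normality rules in SAP 8.10.1.1 also apply, through 8.10.4: "If normality assumptions are violated, first the data will be natural log transformed and the log transformed data evaluated for normality", and then "If the data are not normally distributed, a Wilcoxon Rank Sum Test will be used to compare treatment groups", with Hodges-Lehmann estimates of the difference.

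In the protocol (Section 3), the NFS is one of several further non-invasive tests that may be assessed, under a change-from-baseline endpoint. Protocol 9.4.4 calls for descriptive percent change for exploratory endpoints generally, but its modelled outcomes are changes from baseline.

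**The concern.** Percent change has a consistent meaning only when the baseline is positive and well away from zero. The NFS guarantees neither. If the baseline is negative, dividing by it reverses the sign of the change. If it is close to zero, a small change becomes a very large percentage, and at exactly zero the percentage is undefined. A treatment group holding both signs averages quantities that point in opposite directions.

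At stake is one set of outputs. The percent-change table and model for the NFS could disagree in direction with the absolute-change table and model built from the same data, and a reader of the report would have no means of reconciling them.

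**Working it through.** **Inputs.** The formula is from SAP 8.10.4.3, and the change and percent-change definitions are from SAP 4.5. Eligibility limits are from protocol 5.1 and 5.2: age 18 to 75, BMI at least 25, platelets at least 150, albumin at least 3.3, with or without diabetes. The documents give no NFS distribution, effect size or SD, so there is no plan figure to reproduce. Patient profiles and populations below are assumptions. A fall in this fibrosis score is read as improvement.

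NFS = -1.675 + 0.037 × age + 0.094 × BMI + 1.13 × diabetes + 0.99 × AST/ALT - 0.013 × platelets - 0.66 × albumin

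**Step 1: can eligible patients have either sign?** Yes.

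- Age 18, BMI 25, no diabetes, AST/ALT 0.4, platelets 400, albumin 5: -1.675 + 0.666 + 2.350 + 0 + 0.396 - 5.200 - 3.300 = -6.763.
- Age 75, BMI 45, diabetes, AST/ALT 1.2, platelets 150, albumin 3.3: -1.675 + 2.775 + 4.230 + 1.130 + 1.188 - 1.950 - 2.178 = +3.520.

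**Step 2: same improvement, three patients.** BMI falls by 1 and platelets rise by 15, so the change is -0.094 - 0.195 = -0.289 for each.

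| Patient (age, BMI, diabetes, AST/ALT, platelets, albumin) | Baseline | Later | Percent change |
|---|---|---|---|
| A: 50, 35, no, 0.70, 250, 4.4 | -1.996 | -2.285 | -0.289 / -1.996 = +14.5% |
| B: 62, 40, yes, 0.90, 200, 4.2 | +1.028 | +0.739 | -0.289 / 1.028 = -28.1% |
| C: 58, 36, yes, 0.75, 245, 4.3 | -0.296 | -0.585 | -0.289 / -0.296 = +97.8% (unrounded baseline) |

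The mean absolute change is -0.289. The mean percent change is (14.5 - 28.1 + 97.8) / 3 = +28.1%, the opposite direction.

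**Step 3: near zero.** A fall of 0.3 from -0.05 gives -0.3 / -0.05 = +600%; from +0.05 it gives -600%.

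**Step 4: do the model or the fallback repair it?** No. For a constant change d, percent change is 100 × d / baseline, a curve that breaks at zero, so a linear baseline covariate cannot remove the problem. The natural log is undefined for negative values, which both change and percent change will contain. Ranking percent changes limits the outliers but keeps the reversed signs.

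**Step 5: illustrative frequency.** Simulated baselines within the eligibility limits:

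| Assumed population | Mean (SD) | Negative | Within 0.1 of zero |
|---|---|---|---|
| Younger, 30% diabetic | -2.23 (1.14) | 97% | 1% |
| Central (mean age 50, BMI 36, 50% diabetic) | -1.33 (1.19) | 87% | 4% |
| Older, heavier, 70% diabetic | -0.11 (1.06) | 53% | 7% |
| Extreme (mean age 62, BMI 40, 90% diabetic) | +0.96 (0.89) | 14% | 5% |

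That is about 1 to 6 of 80 patients within 0.1 of zero.

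**Step 6: illustrative trial results.** Central population, assumed effect -0.3, SD of change 0.4, 20 vs 10, 3,000 runs, strata omitted. ANCOVA on change gave a median difference of -0.30 with 44% nominal power. ANCOVA on percent change gave a median difference of +19 percentage points with a median standard error of 55, the wrong sign in 65% of runs, and p < 0.05 in 5%.

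A similar central population at 20 vs 10 shows how far such rates move:

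- Effect -0.1, SD 0.3: wrong sign in 59% (ANCOVA) and 69% (Hodges-Lehmann).
- Effect -0.3: Wilcoxon significant in the wrong direction in 28% with SD 0.3 and 17% with SD 0.4.
- Effect -0.3 in an older, heavier population with about half the baselines negative: both wrong-sign rates about 50%, wrong-direction Wilcoxon significance 2%. That is noise rather than reversal.

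**The case against.** The strongest reply is that little depends on this output. The NFS is exploratory and optional. Its absolute change receives the same descriptive and ANCOVA treatment and is unaffected. It is not in the dose-response list of SAP 8.10.8, has no responder definition, and plays no part in the Part 2 decision (SAP 8.3). All of this stands and limits the importance of the point.

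The SAP also has general flexibility. Section 4.4 allows transformations, Section 1 allows changes documented in the study report, and Section 8.6 labels all testing nominal. None of these corrects a reversed sign in a pre-specified output; they only make late repair possible.

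A reader might infer that the score is usually negative here, so that improving patients will generally appear to worsen. The documents do not support that. They give no case mix, and patient B, with a positive baseline, gets the correct sign. A reader might also infer that the plan would probably report benefit as harm. That rests on an assumed effect. Age and diabetes are fixed at consent, so a 0.3-point fall from one component needs BMI down about 3.2 (0.3 / 0.094), platelets up about 23 (0.3 / 0.013) or AST/ALT down about 0.30 (0.3 / 0.99). Nothing in the documents indicates such a shift at 12 weeks. The larger wrong-direction significance rates also arise only if the rank-based fallback is used.

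**Conclusion.** The point holds on the SAP's own formulas. Percent change in the NFS reverses sign for every patient with a negative baseline and is unbounded near zero. Its group descriptives, ANCOVA and Wilcoxon/Hodges-Lehmann results are therefore uninterpretable and can contradict the absolute-change analysis. This needs no majority of negative baselines: a mixture of signs or a few values near zero is enough.

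The frequency of reversal is unknown. The range of about 14% to 97% negative baselines, and every simulated error rate, rests on assumed populations, effects and SDs and is illustrative only.

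The damage is limited to one redundant output of an exploratory, optional score. No primary or secondary conclusion is affected. It is worth correcting because the SAP commits to producing the output and the correction is simple.

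**What to change.** Add to SAP 8.10.4.3, in these or similar words:

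> The NAFLD fibrosis score will be summarised and analysed as absolute change from baseline only. Percent change will not be derived, because the score can be zero or negative. The natural-log step of Section 8.10.1.1 does not apply to this score; if normality fails, the rank-based method will be used directly.

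The log clause is needed even after percent change is dropped, because absolute changes can be negative too.

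In SAP Section 11, record that descriptive percent change, which protocol 9.4.4 requests for exploratory endpoints, is omitted for this score. No model named in the protocol is lost, since protocol 9.4.4 models change from baseline.

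The cost is a few sentences of SAP text and fewer outputs, with no new data.
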